## 1.0 PURPOSE

## **1.1 Name and Intended Use**

The device used in this study is called the PotenzaTM device.

The intended use of the PotenzaTM device is to collect clinical data for a wide array of dermatologic conditions in which electrocoagulation and hemostasis is a viable mechanism for means of improvement.

## **1.2 Objectives**

- 1. Primary Objectives:
  - Assessment of safety of the study device through the collection of side effects throughout the study.
  - Assessment of the efficacy of the study device through Investigator and subject satisfaction.
  - Evaluation of baseline photographs compared to post treatment images.
- 2. Assessments:
  - Treatment discomfort evaluation
  - Subject treatment experience questionnaire
  - Clinician ease of use questionnaire
  - Clinician and subject satisfaction questionnaire
  - Treatment area photograph blinded evaluation
  - Baseline and short-term histological tissue response as seen in biopsies.

## **1.3 Duration of the Investigation**

The sponsor anticipates that all subjects can be enrolled within 6 months. If subject participates in all required visits, then the subject's participation in this study may last up to 9 months. It is anticipated that it will take approximately 3 months to analyze the data collected during this study. The total duration of this study is anticipated to last approximately 18 months.

## 2.0 PROTOCOL

## 2.1 Protocol Methodology and Analysis

## Methodology:

Subjects are to be enrolled in this clinical study if they are 18 - 55 years old. Up to 120 subjects will be enrolled at 5 study centers. Subjects may receive up to 5 treatments with the PotenzaTM device if they present with conditions such as, but not limited to; Wrinkles, fine lines, crepey skin, acne scars, active acne, enlarged pores, stretch marks, or loose skin on the face, neck and/or body.

Subjects will attend a screening/pretreatment visit which may be performed on the same day as the treatment visit. Subjects will receive up to 5 treatments. All subjects may receive a phone call or attend a visit 24 hours post each treatment and will receive a phone call or attend a visit 1 week (2-10 days) after each treatment to record side effects. Subjects will be required to return for a follow-up visit 30 days after the final treatment. Subjects may also attend an optional follow up visit 90 days after the final treatment. An unscheduled visit or phone call may be performed at any time during the study at the request of the subject or as deemed necessary by the site Investigator.

Analysis:

Upcoming generations are proving to have an interest in aesthetic dermatology treatments and will drive demand for innovated products, procedures, and practice design. Due to this shift in patient base, practices need to evolve to adapt to the newer generational ideologies. There have been rapid advances in RF technology over the past few years and the nonsurgical treatment using this energy source offers great promise to our aging population. Radiofrequency micro needling technology for the treatment of dermatologic conditions needs to be further investigated to optimize treatment parameters for safe and effective non-ablative treatments.

Relevance: Does not apply to this study – feasibility study.

Testability: Does not apply to this study – feasibility study.

Compatibility: Does not apply to this study – feasibility study.

Predictive power: Does not apply to this study – feasibility study.

## 2.2 Protocol Study Design

This is a prospective, open label, multi-center clinical study

## 2.3 Subject Selection Criteria

Subjects will meet the criteria described below:

Inclusion Criteria:

- A healthy, non-smoking male or female between the age of 18-55 years old.
- Fitzpatrick skin type I to VI.
- Understands and accepts obligation not to receive any other procedures on the treatment area through the length of the study.
- Understands and accepts the obligation and is logistically able to be present for all visits.
- Is willing to comply with all requirements of the study and sign the informed consent document.

Exclusion Criteria:

- Is pregnant or of childbearing potential and not using medically effective birth control, or has been pregnant in the last 3 months, currently breast feeding or planning a pregnancy during the study.
- The subject is currently enrolled in an investigational drug or device trial or has received an investigational drug or been treated with an investigational device within in the area to be treated 6 months prior to entering this study.

- The subject has physical problems such as cardiovascular disorders.
- The subject has a pacemaker.

• The subject has skin infections.

• The subject had previous use of gold thread skin reju

venation.

- The subject has any of the following conditions:
  - Diabetes
  - o Epilepsy
  - Acute disease
  - Dermatitis
- Subjects with electronic implants such as cardiac defibrillator. It may interfere with operation of electronic implants or damage the implants, causing risks.
- The subject has any condition or is in a situation which in the investigators opinion may put the subject at significant risk, may confound study results or may interfere significantly with the subject's participation.

Cautionary Criteria:

- Subjects taking medications for heart disease, hyperlipidemia, and hypertension and patients taking NSAIDs, aspirin, and fish oil. They may have more bleeding than others.
- Malignant disease (excluding skin malignancies)
- Subjects with herpes.
- Hemangioma
- Subjects with autoimmune disease
- Subjects with keloids

Be sure to list all concomitant medications or procedures permitted before, during and after the trial.

Subjects will be recruited for the study through existing patient database and advertisements.

Subject populations will not be eligible to participate in the study if they are vulnerable populations such as; children, pregnant women, prisoners, institutionalized individuals, and any persons requiring a legally authorized representative as part of the consenting process.

Subject population characteristics that will not be eligible to participate in participate in the study include non-English speaking individuals and people who cannot read or comprehend English. Employees of the Investigator will may participate in the study.

#### 2.4 Screening

Subjects will be asked questions about their medical history, may have a limited physical and their inclusion/exclusion criteria will be verified. Discontinuation of any concomitant medications, pretreatment instructions and post treatment instruction will be reviewed with the subject.

Procedure for the Limited Physical Exam:

If the investigator determines that a limited exam is necessary, the exam will be like a basic annual physical exam performed by a primary care doctor to determine general overall health. The limited medical exam may include all or any of the following; vital signs such as blood pressure, heart rate, respiratory rate and body temperature, general appearance, listening to the heart, lungs and abdomen with a stethoscope, head and neck exam, in addition to examining the throat, tonsils, teeth, ears, eyes and nose as well as a neurological exam such as testing muscle strength, reflexes, balance, sensory changes of the extremities and mental state.

#### **2.5 Informed Consent Process and Enrollment**

Subjects will be asked to review the pre and post treatment instructions prior to signing the informed consent and their involvement in the study. Subjects who sign the informed consent will be screened to confirm eligibility and if eligible, will be assigned a subject identification number. Subjects will be de-identified through their subject identification number, which will be stored in a secure location. Subject identification numbers will be generated chronologically and assigned only to subjects who have met all the study selection criteria and have signed the informed consent form. The informed consent will be obtained prior to a subject's involvement in any study related procedures. A subject will be considered enrolled in the study once they have signed the informed consent form. Employees of the Sponsor will be required to sign both the main informed consent form as well as an employee consent form.

[figure not shown]
#### 2.6 Pre-Treatment Procedures

If the subject is of childbearing potential (i.e. females not post-menopausal or not surgically sterile), then they will be asked if they are pregnant, the date of their last menstrual cycle, and perform a pregnancy test. If the treatment is on the abdomen, a urine pregnancy test must be performed before each treatment. A urine pregnancy test may be conducted at the Investigators discretion during the study. If a urine pregnancy test is conducted, then a negative result must be obtained within 24 hours prior to the treatment.

Urine Pregnancy Test Procedure:

- 1. A urine sample is tested mid-stream or by cup sample with an indicator stick.
- 2. Negative results are indicated on the indicator stick.
- The following Pre-Treatment instructions will be reviewed:
  - Remove all jewelry and makeup, including eye makeup, lotions or sun block and wash facial area prior to treatment.
  - For an optimum treatment, keep hydrated by drinking water (at least 8 cups daily) or hydrating fluids, such as Gatorade, and avoid drinking alcohol for several days in advance.
  - For five to seven days prior to treatment, at the physician's discretion, avoid therapies that may cause erythema (redness) or irritation such as Retin A or products containing Isotretinoin, glycolic and or salicylic acid.
  - Shave visible hair from the treatment area. Male beards should be shaved day of treatment. RF follows the path of least resistance and the hair will receive the energy.
- Photographs will be taken prior to the first treatment.

#### **2.7 Treatment Procedures**

- The treatment area will be identified and may be marked with a surgical marker.
- Anesthesia (such as a topical or local), air cooling, and/or Nitronox will be used at the discretion of the Investigator.

(UNO(URE

- A neutral pad will be placed in an area determined by the Clinician to maintain standard energy settings and requires less power from the device during the treatment.
- Test spots may be performed prior to the first treatment. Test spots may be performed prior to the first treatment. It will follow a similar procedure to treatment but only in an inconspicuous place, such as behind the ear, in an area no larger than 2in x 2in.
- The tip will be placed in contact with the skin.
- The entire defined treatment area will then be treated as instructed by the Operator's Manual.
- Parameters may be adjusted throughout the treatment and will determined by the Clinician.
- Subjects will be asked to report the general level of treatment discomfort/pain on a scale of 0 (none) to 10 (maximum intolerable pain).
- Photographs may be taken during treatment.
- Subjects may receive up to 5 treatments every 4 weeks (+/- 2 weeks) which will be determined by the Investigator.
- The additional treatments will follow the same procedure.

## **2.8 Post Treatment Procedures**

- Adverse events will be documented after treatment.
- Photographs may be taken post treatment.
- Clinician ease of use and subject treatment experience questionnaires may be performed.
- The following post treatment instructions will be reviewed:
  - Be careful not to expose area of treatment to external stimulation for at least 2 days after treatment.
    - Avoid ultraviolet rays and apply sunscreen.
    - Do not to scrub the skin or exfoliate for several days after treatment.
  - Refrain from high intensity exercise (such as running, weightlifting, aerobics), hot bath or saunas that may cause increase in skin temperature for 5 days after treatment.
  - Refrain from drinking alcohol or taking medicine that interferes with blood coagulation such as aspirin for 2 weeks after treatment.
  - If heat sensation or erythema (redness) after treatment is bothersome, use an ice pack to the treated area at home.
  - If the skin in the treatment area feels tight or dry, apply plenty of moisturizing cream, such as Neutrogena.
  - After the procedure, inflammation or edema (swelling) may block the pores and acne can temporarily worsen (about 7 days). If acne worsens, do not pick or squeeze as pigmentation changes may occur.
  - Sleep in a semi reclined position for the first 2-3 nights to minimize facial swelling.
  - Apply soothing facial mask as needed.

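### The protocol's 2-week post-treatment stop on aspirin and similar medicine has no exception for prescribed use and no prescriber check

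*Combined protocol and SAP*

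**What the plan says.** Section 2.8 (Post Treatment Procedures) gives one list of instructions to be reviewed after treatment, with no subgroup set apart. One item reads: "Refrain from drinking alcohol or taking medicine that interferes with blood coagulation such as aspirin for 2 weeks after treatment".

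The other relevant provisions are these:

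- **Section 2.3, cautionary criteria:** "Subjects taking medications for heart disease, hyperlipidemia, and hypertension and patients taking NSAIDs, aspirin, and fish oil". The reason given is that such people may bleed more. The risk of stopping the medicine is not mentioned.
- **Section 2.3, exclusion criteria:** "The subject has physical problems such as cardiovascular disorders". A separate criterion lets the investigator exclude anyone judged to be at significant risk. The inclusion criteria require a healthy subject aged 18 to 55.
- **Section 2.4:** "Discontinuation of any concomitant medications, pretreatment instructions and post treatment instruction will be reviewed with the subject".
- **Section 2.5:** "Subjects will be asked to review the pre and post treatment instructions prior to signing the informed consent".
- **Section 2.6, on a different restriction:** "For five to seven days prior to treatment, at the physician's discretion, avoid therapies that may cause erythema".
- **Section 2.7:** "Subjects may receive up to 5 treatments every 4 weeks (+/- 2 weeks", plus a line saying that further treatments are done the same way.
- **Section 2.1:** "Subjects will attend a screening/pretreatment visit which may be performed on the same day as the treatment visit".

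**The concern.** The sentence in section 2.8 does not separate aspirin taken casually from aspirin, an antiplatelet or an anticoagulant that a doctor has prescribed. A subject who follows it to the letter stops a prescribed antithrombotic because the site said so, and nothing in the supplied text has anyone ask the prescriber. Subjects also have reason to follow it: section 2.3 requires willingness to meet all study requirements, and section 12.0 makes failure to follow the investigator's instructions a ground for removal.

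What is at stake is the safety of a few subjects having an elective cosmetic procedure. No endpoint, sample size or analysis depends on it.

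**Working it through.** The plan states no figure on this point. The check has two parts: a comparison of the text, and a count of days.

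**1. Can an affected subject enter?** Section 2.3 places aspirin users under caution, not exclusion, and a caution has a purpose only if some such people are treated. The cardiovascular exclusion bars entry whatever the caution says, so it removes many of those who would have a prescription for an antithrombotic. What remains is anyone on prescribed aspirin or a similar medicine who has no excluded condition and whom the investigator does not judge to be at significant risk.

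**2. Does another section supply the missing step?**

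- Section 2.4 reviews discontinuation of medication with the subject. It does not ask whether stopping is safe, and it does not mention the prescriber.
- Section 2.5 puts the instructions before the subject ahead of consent. That is notice, not a medical check.
- Section 2.3 contains a line calling for permitted concomitant medications to be listed. No such list appears in the supplied text, and the schedule in section 2.13 has no concomitant-medication row.
- Section 2.1 allows screening on the day of first treatment. The footnote in section 2.13 allows the same but also asks for at least 30 days beforehand. An interval in which to consult a prescriber is therefore not assured.
- The pre-treatment list in section 2.6 contains no aspirin stop. Continuing prescribed aspirin after treatment would therefore contradict nothing in that list.

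**3. How long is the stop?** The inputs are 14 days per stop (section 2.8), at most 5 treatments, and an interval of 28 days plus or minus 14, so 14 to 42 days (section 2.7). That the stop repeats after each treatment is an inference from section 2.7; section 2.8 does not say so.

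- Total days stopped = 5 x 14 = 70.
- Span from first treatment to the end of the last stop = 4 x interval + 14.
- Days between stops = interval - 14.

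| Interval (days) | Span (days) | Share of span stopped | Days between stops |
|---|---|---|---|
| 14 | 4 x 14 + 14 = 70 | 70/70 = 100% | 0 |
| 28 (nominal) | 4 x 28 + 14 = 126 | 70/126 = 56% | 14 |
| 42 | 4 x 42 + 14 = 182 | 70/182 = 38% | 28 |

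Fewer treatments give proportionately fewer days; one treatment gives 14.

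**The case against.** The strongest reply is that the operative text is out of sight. Section 7.0 lists the consent form and the pre- and post-treatment instructions as the materials given to subjects. Neither is supplied, and advice to ask a doctor before stopping would naturally sit there. This stands. A reader might infer that the trial has no prescriber check anywhere, but the documents support that only for the protocol text.

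The second reply is that section 2.3 nearly closes the gap. This stands in large part. A reader might infer from the caution on heart-disease medication that cardiac patients will be enrolled and told to stop their treatment. The documents do not support that, because the underlying condition would normally meet the cardiovascular exclusion. The residual group is small, but it is not shown to be empty.

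Third, sites keep in touch with subjects. There is a call or visit about 1 week after each treatment (section 2.9), and subjects may contact the investigator at any time (section 14.0). Silence in the protocol is not proof that anyone would stop without advice. That is fair, but none of these contacts is an exception or a prescriber check.

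Fourth, the day count measures calendar time, not harm. This also stands. One might read 70 unbroken days as the expected exposure. It requires all five optional treatments at the shortest permitted spacing, in a subject on prescribed medicine who complies literally.

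Two supporting arguments carry little weight. The discretion clause in section 2.6 concerns irritant skin therapies before treatment, so it says little about what section 2.8 intends. Same-day screening matters only indirectly, because the stop begins after treatment and is disclosed before consent.

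**Conclusion.** The point holds for the protocol text as supplied. Section 2.8 tells subjects to stop medicine affecting coagulation for 2 weeks, section 2.3 allows aspirin users in under caution, and no supplied section exempts prescribed use or involves the prescriber.

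It is minor, and best classed as a cheap improvement. The stop is 14 days after one treatment and at most 70 days over five, assuming that it repeats each time. The number of subjects affected cannot be derived from the documents; none is assumed here, and it should be small. Efficacy conclusions are untouched.

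The conclusion rests on two assumptions: that the instruction sheet and consent form do not already contain the exception, and that at least some subjects on prescribed antithrombotics pass the exclusions. If those materials do contain it, what remains is to bring section 2.8 into line with them.

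A reader might go further and infer that anyone whose prescriber refuses a stop must not be treated. The documents do not require that. Section 2.3 treats aspirin use as a matter for caution, and an automatic bar would turn that caution into a new exclusion.

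**What to change.** Reword the item in section 2.8, and the matching line in the subject instructions, to:

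> Refrain from alcohol, and from non-prescribed aspirin or other non-prescribed medicine that interferes with blood coagulation, for 2 weeks after each treatment. Do not stop prescribed aspirin, antiplatelet or anticoagulant medicine unless your prescriber has agreed.

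In section 2.4, have the site record any prescribed antithrombotic at screening and ask about changes at each treatment visit, so that a prescription started during the study is also picked up. The investigator then decides, under the existing caution and significant-risk exclusion in section 2.3, whether to treat a subject who stays on the medicine. Section 2.3 itself needs no change.

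The cost is one amendment with IRB approval, a short entry in the case report form and a question at visits that already take place. No visits are added. The downside is possibly slightly more bleeding or bruising in the few subjects who continue prescribed medicine; section 2.15 already lists pinpoint bleeding and bruising as possible adverse effects.

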## 2.9 Follow Up

- All subjects may receive a 24 hour phone call or attend a visit post each treatment and will receive a phone call or attend a visit 1 week (2-10 days) after each treatment to record side effects.
- The study subjects are required to return to the investigative site for a follow-up evaluation at 30 days post last treatment.

(UNO(URE

- Subjects may be asked to return for an optional follow up visit 90 days post last treatment.
- Photographs will be taken, subject and physician questionnaires will be performed, and adverse events will be documented at all follow up visits.
- Some subjects may have an incomplete response or no response by the end of the study. At the end of the study, treatments using an FDA approved/cleared treatment method may be discussed with the subject and obtained at the cost of the subject.

#### **2.10 Biopsy Portion of the Study**

- Up to 6 subjects will enroll in the biopsy portion of this study. If the subject has enrolled, the following will also be performed:
  - Biopsies will be taken from the test spot area day of treatment and may be taken 0-24 hours, 25-48 hours, 3-7 days, and 30 days post treatment.
  - Biopsy subjects may receive up to 2 biopsies at each visit, totaling 10 biopsies.
  - A local anesthetic, such as lidocaine, may be injected to the area prior to biopsy.
  - A 2 mm or 3mm punch biopsy (based on Physician assessment) will be taken from the treatment area.
  - Sutures will be uses to close the incision site.
  - The subject will be required to attend a 1 week (7-14 days) post the 7 day biopsy visit and a 1 week (7-14 days) post 30 day biopsy follow up visit to remove the sutures and assess side effects.
- The following post biopsy treatment instructions will be reviewed:
  - Slight redness, initial tenderness to the wound site is normal; however, if you experience more redness, swelling, pain, pus, or drainage contact the study site immediately.
  - If the biopsy site begins to bleed, apply direct pressure for 10-20 minutes. If it continues to bleed, call the study site immediately.
  - Keep the wound dry today and remove bandage in 24 hours and leave off.
  - Avoid hot tubs, pools, and ocean until sutures are removed. Avoid soaking in water until 14 days after your biopsy.
  - When showering, wash carefully and do not scrub or traumatize the treated skin, or allow spray of shower to strike the skin directly. If the skin is treated harshly, this can increase the risk of scarring.
  - After showering, lightly pat dry the wound or let it air dry, then cover the biopsy site with an application of Vaseline (or petroleum jelly) at least 1-2 times daily. Keeping the wound moist reduces infection, minimizes scarring, and prevents crust formation over the wound.
  - Band-Aids (or any generic Adhesive Bandages) may be used for sleeping or in daily routines where the area may be rubbed/irritated. Whenever possible, keep Band-Aid (or generic Adhesive Bandage) off of the area and keep the area moist with Vaseline (or petroleum jelly) as previously described but do not allow drying out and forming a hard scab.

- For any wound discomfort, you may take Tylenol as needed, or use cold compresses for up to 20 minutes hourly as needed. If using ice, it should be wrapped in a plastic and then a cloth to avoid burning your skin and wetting your bandage.
- Avoid picking at the wound site, which increases risk of infection and scarring.
- In order for the wound to heal properly and not leave bumpy scars, be careful not to
  overstretch the wound site area. As a wound heals, it will be weaker than the surrounding
  skin and can even "pop open" the sutures (stitches) if stretched too much. Sport or
  strenuous exercises that can pull at the wound site are best avoided for at least the next 3
  days and up to one week.
- Return for suture removal within 7 14 days as instructed per study protocol. If applied, Steri-strips must be kept dry as they are more likely to separate when wet. Steri-strips will usually fall off by themselves or you may be advised by the study doctor to remove them when the wound healed.
- ONCE SUTURES ARE OUT: To minimize sore formation and to improve the final appearance of your skin, it is very important to keep the wound site area covered with the Vaseline for the next few days, until there is no more crust forming and the skin has completely healed.
- Temporary discoloration at the wound site is normal and should gradually fade over the next few months. Please protect newly healed biopsied area with SPF and avoid sunburn.

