## CUNO(URE

## **Biopsy Schedule of Visits and Procedures:**

	Biopsy #1	Biopsy #2	Biopsy #3	Biopsy #4	Post Biopsy Visit #1	Biopsy #5	Post Biopsy Visit #2
Procedure	Treatment Visit (control)	0-24 Hours Post Treatment	25-48 Hours Post Treatment	3-7 Days Post Treatment	Follow Up 1 Week Post Biopsy #4 (7-14 Days)	Follow Up 30 Days Post Tx (+/- 1 Week)	Follow Up 1 Week Post Biopsy (7-14 Days)
Biopsy	Х	Х	Х	Х		Х	
Suture Removal					Х		Х
Photographs	Х	Х	Х	Х	Х	Х	Х
Adverse Events Assessment	Х	Х	Х	Х	Х	Х	Х

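### The biopsy schedule permits sutures from Biopsy #1 to stay in until day 21 against a stated 7-14 days, and the first removal visit has no anchor if Biopsy #4 is omitted

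*Combined protocol and SAP*

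**What the plan says.** Three places in the combined protocol and SAP bear on when biopsy sutures come out.

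- **Section 2.10, post-biopsy instructions to subjects:** "Return for suture removal within 7 14 days as instructed per study protocol". The dash between 7 and 14 is lost in the text; I read it as 7-14 days, which matches the windows elsewhere in the section. No biopsy is exempted.
- **Section 2.10, visit text:** "The subject will be required to attend a 1 week (7-14 days) post the 7 day biopsy visit", and a second visit on the same pattern after the 30-day biopsy. These are the only two removal visits described.
- **Biopsy Schedule of Visits and Procedures:** the first removal visit is headed "Follow Up 1 Week Post Biopsy #4 (7-14 Days". The suture-removal row is marked there and at the visit after Biopsy #5, and nowhere else.

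On which biopsies are taken, section 2.10 says: "Biopsies will be taken from the test spot area day of treatment and may be taken 0-24 hours, 25-48 hours, 3-7 days, and 30 days" after treatment. The day-of-treatment biopsy is thus definite and the later four are permissive. The schedule lists Biopsy #1 as "Treatment Visit (control", Biopsy #2 as "0-24 Hours Post Treatment", Biopsy #3 as "25-48 Hours Post Treatment", Biopsy #4 at 3-7 days and Biopsy #5 at 30 days plus or minus one week. Section 2.10 has sutures closing the biopsy site, again with no exception, and limits this part of the study to 6 subjects.

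**The concern.** Biopsies #1 to #3 have no removal visit of their own. Their sutures wait for a visit counted from a later biopsy, so the time in place is the 7-14 day gap plus the delay to Biopsy #4. A site can keep to every window in the schedule and still pass the interval given to the subject.

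The two descriptions of the anchor also differ. The visit text calls it the 7-day biopsy visit, while the schedule allows day 3 to day 7.

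The second difficulty does not depend on how the 7-14 days is read. The one biopsy that is definitely taken has its sutures removed at a visit defined by a biopsy that may not be taken. At stake is a clear, single instruction on a procedure for up to 6 subjects. No endpoint or test depends on it.

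**Working it through.** **Inputs** (days after treatment, from the biopsy schedule; all biopsies are assumed to be counted from the same treatment):

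- Biopsy #1: day 0
- Biopsy #2: day 0-1
- Biopsy #3: 25-48 hours, or day 1.04-2
- Biopsy #4: day 3-7
- Biopsy #5: 30 ± 7, or day 23-37
- Gap from Biopsy #4 or #5 to its removal visit: 7-14 days

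**Stated figure.** For Biopsies #4 and #5 the schedule reproduces the 7-14 days exactly, because the removal visit is counted from the biopsy itself. It does not reproduce it for Biopsies #1 to #3.

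**First removal visit.** Earliest 3 + 7 = day 10; latest 7 + 14 = day 21.

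**Time in place.** Minimum = earliest removal day minus latest biopsy day; maximum = latest removal day minus earliest biopsy day.

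| Biopsy | Minimum | Maximum | Permitted range |
|---|---|---|---|
| #1 | 10 − 0 = 10 | 21 − 0 = 21 | 10-21 days |
| #2 | 10 − 1 = 9 | 21 − 0 = 21 | 9-21 days |
| #3 | 10 − 2 = 8 | 21 − 1.04 = 19.96 | 8 to about 20 days |

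The largest excess over 14 days is 21 − 14 = 7 days.

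**How much of the permitted range complies for Biopsy #1.** In whole days there are 5 possible days for Biopsy #4 and 8 possible gaps, so 5 × 8 = 40 combinations. The sum must not exceed 14:

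- Biopsy #4 on day 3: gaps 7-11 comply (5)
- day 4: gaps 7-10 (4)
- day 5: gaps 7-9 (3)
- day 6: gaps 7-8 (2)
- day 7: gap 7 only (1)

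That gives 15 combinations within 14 days and 40 − 15 = 25 beyond it. This counts what the schedule allows; it is not a probability.

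**With the anchor fixed at day 7, as the visit text words it.** Removal falls on day 14-21. Time in place is 14-21 days for Biopsy #1, 13-21 for #2 and 12 to about 20 for #3.

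**If Biopsy #4 is omitted.** The first removal visit cannot be dated. The second falls between 23 + 7 = day 30 and 37 + 14 = day 51. If Biopsy #5 is omitted as well, no removal visit is defined.

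**The case against.** The strongest reply is that the windows overlap and the nominal plan complies. Both places label the visit as one week after the biopsy. One week after Biopsy #4 on day 3-7 is day 10-14, within 14 days of Biopsy #1 in every case. That stands: a breach needs late use of the permitted window. A reader might infer that the two timings are incompatible, or that sutures from the first three biopsies always stay in too long. The documents support neither.

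Second, the instruction points to the protocol and does not say that the days run from each biopsy. It may simply restate the window of the scheduled visits. That is a fair reading and softens the conflict towards an ambiguity. It does not remove it, because the instruction exempts no biopsy and the schedule runs to day 21 for the first.

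Third, the biopsy schedule marks all five biopsies and both removal visits without calling any of them optional, whereas the main schedule in section 2.13 does label its optional contacts. If Biopsy #4 is skipped, the subject still holds the 7-14 day instruction. Section 2.9 also provides a contact at 2-10 days, and section 2.11 allows unscheduled visits. So day 30-51 is the next *scheduled* removal, not a forecast of what would happen. But the 2-10 day contact may be a phone call and is meant for side effects, unscheduled visits are discretionary, and neither is designated for suture removal. The missing anchor remains.

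Finally, a reader might infer that longer time in place would add biopsy-related adverse events. Section 2.15 lists infection and scarring among biopsy complications, but nothing in the documents links them to how long sutures stay in. That claim is not made here.

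**Conclusion.** The point holds as a minor internal inconsistency with two parts. First, the schedule permits sutures from Biopsy #1 to remain for 10-21 days, up to 7 days past the 14 in the subject instruction, with similar ranges for Biopsies #2 and #3. If Biopsy #4 is on day 7, only a visit exactly 7 days later keeps the Biopsy #1 sutures within 14 days. Second, the first removal visit is undefined when Biopsy #4 is omitted, which the permissive wording "may be taken 0-24 hours, 25-48 hours, 3-7 days, and 30 days post treatment" allows.

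The first part rests on reading the 7-14 days as running from each biopsy. The second rests only on the later biopsies being optional, as section 2.10 words them. At most 6 of up to 120 subjects are affected, and the statistical analysis is not. No view is taken on which removal interval is right.

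**What to change.** Reconcile the visit text and the subject instructions in section 2.10 with the biopsy schedule, so that:

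1. the removal time for every biopsy, including Biopsies #1 to #3, agrees with one stated window, and the text says what that window is counted from;
2. the anchor of the first removal visit is described the same way in the text and the schedule;
3. a removal visit is defined whichever optional biopsies are taken, and the text and schedule agree on which are optional.

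The clinical timing is for the sponsor and investigators to decide. The cost is a wording amendment with the IRB approval that section 21.0 requires, matching changes to any subject materials that repeat the instruction, and possibly one existing visit re-timed, in at most 6 subjects. Sample size, endpoints and analyses are unchanged.
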